### **8.4 Adherence to intervention**

The percentage of glasses wear adherence per week will be reported for the duration of the trial.

## **9. COMPARATIVE ANALYSES**

### **9.1 Analysis of primary and secondary outcomes**

We will calculate the Cox proportional hazard ratio for the rate of retention between Treatment and Control groups with and without adjustment for the following co-variates: age, work tenure, spectacle wear compliance, self-reported self-efficacy, rural vs urban factory, hostel vs non hostel residence, marital and parental status, skill grade (if not too highly colinear with work tenure), work attendance. Linear regression analyses will be performed on potential determinants of primary and secondary outcomes. The study group and all significant variables with p values less than 0.20 in simple regression analyses will be included in multiple regression models. Histograms, normal quantile plots (QQ Plot), and the Shapiro-Wilk normality test will be used to test the normality assumption in regression models. For the Visual Quality of Life (THRIVE) tool, a composite score (eleven items) and near activities sub-score (five items) will be created on 0–100 scales. Intervention costs will comprise the screening test, glasses (and any replacement thereof) as well as direct and indirect costs to the company for facilitating workplace-based sight tests. We will report cost effectiveness distinguishing between study costs and program costs.

The analysis of primary and secondary outcomes will be adjusted for the minimisation factors (age, work tenure at the textile factory, efficiency during baseline assessment) to

account for the correlation between treatment groups introduced by balancing the randomisation. Both the crude unadjusted and adjusted estimates will be presented, but the primary inference will be based on the adjusted analysis.

For multiple imputation of missing data in assessing primary outcomes we will create 20 copies of the data, in which missing values shall be imputed by chained equations, and the datasets will be averaged.

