## 4.6 Definition of primary and secondary outcomes

### 4.6.1 Primary outcome

The primary objective of the study is to estimate the effect of the provision of free reading glasses on the retention of textile workers employed in Shahi's sewing department. The time-to-event endpoint for PROSPER III is defined as the time between randomization to

Intervention or Control Group and loss of employment at Shahi. Employment status for each participant will be assessed from trial entry to closure as recorded in Shahi's Human Resource Management Database.

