#### 4.6.2 Secondary outcomes

The secondary outcomes are:

- reasons given by supervisor and colleagues of former sew-ers (separately) for workers no longer being employed at Shahi
- proportions of sew-ers who state they are satisfied or very satisfied with work, feel valued or very valued at work, and are likely or very likely to stay with current employer
- change in self-assessed productivity
- self-report of having been approached by their assigned Captain and/or a supervisor
- change in attitude towards eye health, glasses wear and uptake of eyecare services
- changes in skill grade and associated change in wage
- adherence with spectacle wear
- Quality of Life using the THRIVE Near Vision Quality of Life tool.
- intervention cost-effectiveness

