### 4.10.2 Data collection during trial

Wage and employment status data will be collected on a daily basis from Shahi's Human Resource division. Employment status data will be assessed on a weekly basis over the 18-month intervention period. Intervention costs will be collected by VisionSpring and assessed at the end of the trial intervention period. Secondary outcome data will be collected using the following data collection forms

- Baseline Assessment (following eye examination)
- Endline Assessment (at the end of the 18-month intervention period)
- Spectacle Wear Compliance (on a weekly basis over the 18-month intervention period)
- Self-assessment of productivity by workers enrolled in the trial (once at the start and at the end of the study)
- Supervisor assessment of worker productivity for workers enrolled in the trial (once at the start and at the end of the study)
- Identification of trial participants leaving the employ of Shahi will occur every two months and telephone interviews will be scheduled in two phases (7 months and 16 months after the start of assessment period)

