## 6. ADHERENCE TO THE INTERVENTION

Adherence to the intervention will be assessed through observation of spectacle wear while working. Adherence will be measured surreptitiously on a weekly basis. The enumerators assessing spectacle wear compliance are GBL staff members familiar to Shahi workers but are not revealed to be collecting glasseswear adherence data to ensure minimum modification of compliance behaviour in present of enumerators.

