## 7. ANALYSIS POPULATIONS

### 7.1 Primary analysis strategy

All outcomes will be assessed by Intention-to-treat (ITT): participants will be analysed in the groups into which they were randomly allocated, i.e. comparing the outcomes of all workers allocated to the Intervention Group with workers allocated to the Control Group, regardless of allocation received.

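### Section 9.1 adjusts the primary Cox model for spectacle-wear compliance, which is measured after randomisation, and does not say which adjusted model carries the primary inference

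*SAP*

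**What the plan says.** **Two adjustment sets in SAP 9.1.** The Cox hazard ratio for retention is to be calculated "with and without adjustment for the following co-variates: age, work tenure, spectacle wear compliance, self-reported self-efficacy", followed by factory location, hostel residence, family status, skill grade and work attendance. A later paragraph says that the analyses of primary and secondary outcomes "will be adjusted for the minimisation factors (age, work tenure at the textile factory, efficiency during baseline assessment"). It then states: "Both the crude unadjusted and adjusted estimates will be presented, but the primary inference will be based on the adjusted analysis". The section does not say which of the two sets this refers to. Between them stands a rule, worded for linear regression but naming primary outcomes and study group, that carries variables with p below 0.20 into multiple regression models.

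**What compliance is.** Section 4.10.2 lists "Spectacle Wear Compliance (on a weekly basis over the 18-month intervention period"). Section 6 defines it as observed wear while working: "Adherence will be measured surreptitiously on a weekly basis". Section 4.6.2 counts "adherence with spectacle wear" among the secondary outcomes. Under 4.5 the Control group gets no trial glasses until the assessment period ends.

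**What the trial is to estimate.** The primary objective in 4.6.1 is to "estimate the effect of the provision of free reading glasses on the retention of textile workers". Section 7.1 applies intention-to-treat to all outcomes: "participants will be analysed in the groups into which they were randomly allocated".

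**How workers are allocated.** Section 4.9 describes blocks of four within four strata formed by age and tenure. It describes neither minimisation nor an efficiency factor.

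**The concern.** Compliance is a consequence of allocation. Intervention workers are handed glasses, and Control workers can wear them only if they buy their own. Holding compliance fixed removes whatever part of the effect works through wearing glasses, which is the main route by which they could help. It also compares workers with equal wear but different allocation, and these need not be alike in prognosis. In addition, wear at work can be observed only while a worker is still employed, so the covariate's observation window depends on the outcome. The plan does not say how a weekly measure would enter the model.

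Work attendance raises the same question. It has no time point and is not among the baseline characteristics in 8.2. If measured during follow-up, it too may be affected by the glasses.

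If the compliance list is taken as the adjusted analysis, the headline hazard ratio does not answer the question in 4.6.1, and a real benefit could be reported as none. The crude estimate would still be shown, but 9.1 says that it does not carry the inference.

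**Working it through.** **1. The plan's own figure.** Inputs from 4.8: HR 0.8, two-sided 5%, 80% power, 1:1 allocation. Schoenfeld events = 4(1.960 + 0.842)² / (ln 0.8)² = 631. Divided by an overall event probability of 0.50, this gives 1,262, against the stated 1,260. The sample size is reproduced.

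**2. Arm alone at 18 months.** Control retention is 40% and HR is 0.8. Expected leavers = 630 × 0.60 + 630 × (1 − 0.40^0.8) = 378 + 327 = 705. SE of the log HR ≈ 2/√705 = 0.075. Power = Φ(0.223/0.075 − 1.96) ≈ 84%. Simulation gave HR 0.80, SE 0.076 and power 83–85%.

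**3. Adding compliance.** The SAP gives no expected wear for this trial, so three wear patterns are assumed. For 1:1 allocation the variance inflation of the arm term is VIF = 1 + (Δ/2)²/w, where Δ is the difference in mean wear and w the average within-arm variance:
- 0.8 (SD 0.2) v 0.03 (SD 0.05): 1 + 0.1482/0.02125 = 8.0
- 0.7 (SD 0.25) v 0.05 (SD 0.10): 1 + 0.1056/0.03625 = 3.9
- 0.6 (SD 0.3) v 0.10 (SD 0.15): 1 + 0.0625/0.05625 = 2.1

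The simulation used exponential leaving times, censoring at 18 months, 630 per arm, one beta-distributed wear value per worker and 2,000 trials per cell. Wear was unrelated to prognosis within arm. Results for the arm term with compliance in the model:

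| Mean wear | SE | None of effect through wear | Half | All |
|---|---|---|---|---|
| 0.8 v 0.03 | 0.22 | HR 0.80, power 17% | HR 0.89, 8% | HR 1.00, 5% |
| 0.7 v 0.05 | 0.15 | HR 0.80, power 30% | HR 0.89, 12% | HR 1.00, 5% |
| 0.6 v 0.10 | 0.11 | HR 0.80, power 51% | HR 0.89, 16% | HR 1.00, 5% |

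In the last column the 5% is the two-sided rejection rate, of which about 2% favours glasses. By hand, multiplying 0.075 by √VIF gives powers of 18%, 32% and 53% for the first results column, in line with the simulation.

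**4. Other wear levels.** In 150 runs per case, with the effect acting through wear and none worn in Control, mean Intervention wear of 84.5% (the closeout figure that 4.2 reports for the earlier tea-worker trial) moved the HR from 0.81 to 1.02, SE from 0.075 to 0.357 and power from 79% to 5%. With 60% wear, the HR moved from 0.81 to 1.02 and power from 80% to 6%.

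**5. Wear linked to prognosis.**
- No true effect, and Intervention wear rising directly with a prognostic factor (log-hazard 0.2 per SD): the arm-only HR was 1.01 and 1.00 with 4.7% rejection. With compliance added it was 1.66 (60% wear) and 3.44 (84.5% wear), with rejection of 93% and 96%. This is an extreme link (150 runs).
- A direct HR of 0.8, and a prognostic factor (log-hazard 0.4 per SD) correlated 0.5 with wear rank: arm-only HR was about 0.81. With compliance it was 1.72, 1.37 and 1.14 for the three patterns in step 3 (300 runs).

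**6. The corrected model.** Arm plus the age and tenure strata, four strata of 315, assumed stratum HRs (age/tenure) of 1/1, 0.8/0.7 and 0.7/0.5, 2,000 trials each: HR 0.80, SE 0.075–0.076, power 84–85%, type I error 4.5–5.9% (simulation error about ±1 point).

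**The case against.** The strongest reply is that the sentence on primary inference directly follows the one on age, tenure and baseline efficiency, all of which are baseline variables. The compliance list stands a paragraph earlier, separated by text on linear regression, quality of life and costs. On that reading the headline result is a sound intention-to-treat estimate, and the compliance-adjusted one is a badly labelled extra.

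That is the more natural reading, but the text does not settle it. The contrast of unadjusted and adjusted estimates equally echoes the with-and-without wording of the first list. The second set is also described as minimisation factors, which do not exist in the 4.9 design, so it cannot be matched to the allocation. Even on the benign reading, a compliance-adjusted hazard ratio for the primary outcome stays planned with no exploratory label, because section 12 treats as exploratory only analyses that are not specified.

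The sizes are fairly challenged. They rest on assumed wear and mechanism, and the table in step 3 assumes wear unrelated to prognosis within arm. Relaxing that, as in step 5, makes the distortion worse and can reverse its direction. The table is therefore illustrative and leaves out the worst case.

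Some related points are smaller. Adjusting for baseline efficiency causes no bias; only its label is wrong. The p<0.20 rule may be meant for modelling determinants, but it names primary outcomes and study group, and so sits badly with 9.3, which rejects selection by preliminary tests. For attendance, bias is possible but not shown. The compliance subgroup in 9.2 carries a general caution on power, but it too splits on a post-randomisation variable, and the text does not say whether by factory, worker or arm.

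**Conclusion.** The concern holds. A post-randomisation measure of uptake, itself a secondary outcome, is listed as a covariate of the primary Cox model. The arm term in that model is not the effect set out in 4.6.1 and 7.1, whatever the wear level turns out to be. Separately, the plan does not fix which adjusted model carries the inference.

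The size depends on assumptions that the SAP does not supply. Under the step 3 patterns, power falls from about 84% to between 5% and 51%, and the hazard ratio lies between 0.80 and 1.00. If wear tracks prognosis, the hazard ratio can exceed 1 although glasses help or do nothing. The harm reaches the headline result only if the first list is taken as the adjusted analysis. Because the primary analysis is at stake, this must be settled before the data are analysed.

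**What to change.** In 9.1, name one primary model: Cox regression of time to leaving on arm plus the 4.9 stratification factors, age and tenure. Further baseline covariates, such as baseline efficiency, may be added if listed in advance. State that this model is the adjusted analysis that carries the primary inference.

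Then:
- remove compliance from every model that compares the arms, and study wear in a separate adherence analysis labelled exploratory;
- use work attendance only as a pre-randomisation value, or drop it;
- replace the reference to minimisation with the 4.9 strata;
- state that the p<0.20 screen is not used for arm comparisons;
- in 9.2, replace the compliance subgroup with the exploratory adherence analysis and define its measure and unit.

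The cost is a wording change to 9.1 and 9.2. The primary model needs no new data, and the sample size of 1,260 stands: 630 events give 80.0% power, and the roughly 705 expected by 18 months give 84%.

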## 9.3 Sensitivity analysis

We will conduct additional “post-hoc” analyses in which we will adjust for additional pre-specified potential confounders (table 1 below). The pre-specified confounders will be included in the models even when no baseline imbalance exists. We have limited the inclusion of potential confounding variables to those that we surmise to be the most important based on the investigators’ assessment of clinical plausibility. This approach has been chosen since confounder selection strategies which are based on collected data, for example selecting confounders using preliminary statistical tests, result in models with poor statistical properties such as incorrect type I error rates. Those confounders that are highlighted as having a significant impact in the subgroup analyses will also be included in these analyses to assess the impact on the treatment effect.

Table 1:

Level	No.	Confounder
Patient	1	Age (years, continuous)
	2	Sex (Male/Female)

Site	3	Rural/Urban
------	---	-------------

Some workers leave the workforce temporarily to take up higher paying seasonal or temporary work, with the intention of returning to the factory workforce after several months away. These workers undergo rigorous performance testing before being permitted to re-join the factory workforce. As the reason for leaving the workforce temporarily is not related to reduced productivity, we feel it is important to include a sensitivity analysis of the primary outcome that takes seasonal and temporary work patterns into account. To this end, in addition to the pre-specified sensitivity analyses outlined above, we will conduct supplementary analyses of the primary outcome that will focus on participants who exited the factory to pursue other seasonal or temporary employment opportunities at the conclusion of the 18-month primary data collection period, but who return to their positions in the factory within a four-month period after the conclusion of primary data collection.

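### Sex is in neither covariate set that could carry the primary inference (SAP 9.1), although 9.3 counts it among the most important confounders; adding it is a small, nearly free improvement

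*SAP*

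**What the plan says.** SAP 9.1 describes adjustment twice.

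- **Long Cox list:** "age, work tenure, spectacle wear compliance, self-reported self-efficacy, rural vs urban factory, hostel vs non hostel residence, marital and parental status", followed by "skill grade (if not too highly colinear with work tenure), work attendance".
- **Short set:** the outcome analyses are to be "adjusted for the minimisation factors (age, work tenure at the textile factory, efficiency during baseline assessment").

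The paragraph on the short set ends by stating that "the primary inference will be based on the adjusted analysis", without saying which of the two sets is meant. Between the two, 9.1 also describes linear regressions on determinants of outcome, in which "all significant variables with p values less than 0.20 in simple regression analyses will be included in multiple regression models".

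SAP 9.3 plans further models, called post-hoc, that will "adjust for additional pre-specified potential confounders (table 1 below"). The authors say they have "limited the inclusion of potential confounding variables to those that we surmise to be the most important" on grounds of clinical plausibility. Table 1 has three rows: age, sex and rural/urban site. Section 9.3 also brings in factors that stand out in the subgroup analyses.

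Elsewhere, sex is a baseline characteristic (8.2) and the first subgroup factor (9.2). It is not a stratification factor (4.9 uses age and tenure).

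**The concern.** The plan applies two standards to one variable. In 9.3 sex passes a stated test of importance. In 9.1 it is missing from a list of nine items and from a list of three, and no reason is given. Whichever set the sponsor means, the model behind the headline result omits a baseline variable that the investigators themselves regard as one of the most important, and the design does not balance for it.

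In a Cox model, omitting a prognostic baseline variable pulls the estimated treatment hazard ratio slightly towards 1 and loses some power. The trial is planned at 80% power, so a point or two is worth having when it costs nothing. Fixing the matter now also removes a later choice between headline models with and without sex.

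**Working it through.** **1. Which variables are where**

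| Table 1 variable (9.3) | Long list (9.1) | Short set (9.1) |
|---|---|---|
| Age | yes | yes |
| Sex | no | no |
| Rural/urban | yes | no |

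Sex is in 0 of 2 sets. Against the long list, Table 1 adds only sex. Against the short set it adds sex and rural/urban.

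**2. Could sex enter 9.1 another way?** Only through the p < 0.20 screen. That is written for the linear regressions on determinants, and it depends on the data. Section 9.3 itself rejects selection of that kind because it distorts type I error. The screen does not fix sex in the primary Cox model.

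**3. The plan's own sample size (4.8).** Inputs: hazard ratio 0.8, two-sided 5%, 80% power, 1:1 allocation. Schoenfeld events = 4(1.960 + 0.842)² / (ln 0.8)² = 631. With 50% of workers leaving, N = 631 / 0.50 = 1,262, against 1,260 stated. The figure reproduces. The formula has no covariate term, so adding sex leaves N unchanged.

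**4. Expected events at 18 months.** Control retention is 0.40 (4.8). Under a hazard ratio of 0.8, Intervention retention is 0.40^0.8 = 0.480. Events = 630 × 0.60 + 630 × 0.52 ≈ 705.

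**5. What omitting sex costs.** The SAP gives neither the sex mix nor leaving rates by sex, so both are assumed: 10% to 50% of workers in the higher-leaving sex, and a sex hazard ratio of 1.25 to 2.0. The treatment hazard ratio given sex is 0.80, leaving times are exponential, overall Control retention at 18 months is 40%, and N = 1,260. The hazard ratio without sex is the large-sample solution of the Cox score equation with sex left out. Power is the Schoenfeld power at the resulting events.

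| Share | Sex HR | Treatment HR without sex | Power with sex | Power without sex |
|---|---|---|---|---|
| 10% | 1.25 | 0.8003 | 84.2% | 84.1% |
| 10% | 1.5 | 0.8011 | 84.2% | 83.8% |
| 10% | 2.0 | 0.8034 | 84.3% | 82.9% |
| 30% | 1.25 | 0.8007 | 84.2% | 83.9% |
| 30% | 1.5 | 0.8023 | 84.3% | 83.3% |
| 30% | 2.0 | 0.8071 | 84.3% | 81.3% |
| 50% | 1.25 | 0.8008 | 84.2% | 83.9% |
| 50% | 1.5 | 0.8026 | 84.3% | 83.2% |
| 50% | 2.0 | 0.8075 | 84.3% | 81.2% |

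The loss is 0.1 to 1.1 points at a sex hazard ratio of 1.25 to 1.5, and 1.4 to 3.2 points at 2.0.

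**6. Cross-check by simulation** (1,500 trials per scenario, same assumptions). At 20% share and sex hazard ratio 1.5, power was 84.0% with sex and 83.3% without. At 20% and 2.0 it was 85.7% and 83.4% (hazard ratios 0.798 and 0.803). At 40% and 2.0 it was 84.4% and 80.3% (0.800 and 0.809). The two methods agree to within about a point.

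**The case against.** The strongest reply is that this is an analyst's choice. Adjusting the primary model for balancing factors, and keeping other prognostic variables for a pre-specified sensitivity model, is accepted practice. A variable named for sensitivity work need not also be in the primary model. The harm is small even on unfavourable assumptions: the lowest simulated power without sex, 80.3%, still meets the 80% target. All of this stands, and it is why the point is an improvement and not an error. It does not explain why sex is left out while variables outside the most-important list are included.

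A reader might infer three stronger things that the SAP does not support.

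- **That the primary result would be confounded by sex.** Randomisation keeps the test without sex valid. The shift in hazard ratio is the usual gap between estimates with and without conditioning on a prognostic variable.
- **That the plan ranks sex above the 9.1 covariates.** The numbers in Table 1 are row labels. Section 9.3 limits its list to important variables but does not compare them with those in 9.1.
- **That the 9.3 analysis is redundant or cannot do its job.** Two of three variables repeat only against the long list. The sentence on primary inference closes the paragraph on the short set, and if that set is primary, only age repeats. Section 9.3 also admits factors from the subgroup analyses, some of which (degree of presbyopia, presenting near acuity) are in neither 9.1 set. Carrying age forward into a sensitivity model is ordinary.

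**Conclusion.** The point holds in limited form. Sex is in neither adjustment set in 9.1, while 9.3 treats it as one of a few leading confounders and confines it to an analysis called post-hoc. This is true whichever set is primary.

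The gain from including sex is small: about 1 point of power or less if the sex hazard ratio is 1.25 to 1.5, and roughly 1 to 4 points if it is 2.0, with the treatment hazard ratio attenuated from 0.80 to at most about 0.81. If sex does not predict leaving, nothing is gained and practically nothing lost. These figures rest on an assumed sex mix, assumed sex effects, exponential leaving times and the design assumptions in 4.8. The absence of sex from both lists rests on the text alone.

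**What to change.** In 9.1, add sex (male/female) as a pre-specified fixed baseline covariate in the adjusted Cox model that carries the primary inference, and name that model, since the text leaves open which of the two sets it is. If the sponsor prefers to leave sex out, give the reason.

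In 9.3, state that the sensitivity model extends the primary model's covariates and does not replace them. If it replaced them, it would drop tenure, which is a stratification factor. Table 1 can keep age and rural/urban: removing them gains nothing and, once sex is in a primary model that already holds the other two, would leave the table empty.

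The cost is SAP wording and one degree of freedom against about 705 expected events. Sex is already a listed baseline characteristic, so no new data are needed, and N stays at 1,260.

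### Section 9.1 prescribes linear regression with normality checks for determinants of every outcome, but retention is a censored time and several secondary outcomes are yes/no; Cox still governs the primary comparison

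*SAP*

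**What the plan says.** SAP section 4.6.1 sets the type of primary outcome: "The time-to-event endpoint for PROSPER III is defined as the time between randomization" and loss of employment at the company. For the comparison of arms, section 9.1 names a suitable method: "We will calculate the Cox proportional hazard ratio for the rate of retention between Treatment and Control groups", with and without covariates.

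Section 9.1 then adds a further analysis: "Linear regression analyses will be performed on potential determinants of primary and secondary outcomes". Its model-building rule is "The study group and all significant variables with p values less than 0.20 in simple regression analyses will be included in multiple regression models", and its diagnostic rule is "Histograms, normal quantile plots (QQ Plot), and the Shapiro-Wilk normality test will be used to test the normality assumption in regression models". Neither rule is limited to a class of outcome.

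The secondary outcomes in section 4.6.2 are of mixed type. They include "proportions of sew-ers who state they are satisfied or very satisfied with work", with matching proportions for feeling valued and for being likely to stay. They also include a self-report of having been approached at work, reasons for leaving, and changes or scores that are closer to continuous. Apart from Cox regression for the arms, linear regression is the only type of model that the SAP names. No logistic, binomial, Poisson or other categorical-outcome model appears.

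**The concern.** Read as written, one continuous-outcome model is fixed for outcomes of at least three types. Two consequences follow.

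- **Determinants of retention.** A linear model of observed time has no place for censoring. The analyst must enter workers still employed as if they left at the end of follow-up, or drop them. The SAP does not say which. Because study group is forced into the multiple regression, the analysis also yields a second group effect on the primary outcome, in months, beside the Cox hazard ratio. The SAP does not say how the two relate.
- **Yes/no secondary outcomes.** The only model available is a linear one whose stated check is normality, which binary data cannot meet. The SAP gives no alternative and no action if the check fails, so the model would be chosen after the data are seen.

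At stake are the reported determinants of retention and the estimates for satisfaction, feeling valued and intention to stay.

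**Working it through.** **Inputs (SAP section 4.8).** Control retention 50% at 12 months and 40% at 18 months; hazard ratio 0.8; two-sided 5%; 80% power; N = 1,260, 630 per group. Follow-up is 18 months (section 4.10.2).

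**The plan's own figure.** Schoenfeld's formula with these inputs gives 631 events. Divided by the 50% Control event rate at 12 months, that is 631 / 0.50 = 1,262, in line with 1,260. The inputs are therefore read as intended. The point itself does not depend on the sample size.

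**Step 1: how much of the primary outcome is censored.** Under proportional hazards, Intervention retention = (Control retention)^HR.

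- Control at 18 months: 0.40, so 630 × 0.40 = 252 workers.
- Intervention at 18 months: 0.40^0.8 = 0.480, so 630 × 0.480 ≈ 303 workers.
- Together: 252 + 303 = 555 of 1,260, or 44%.

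This uses only the 18-month figure and the hazard ratio. It needs no assumption about the shape of the curve.

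**Step 2: what a linear model of time would estimate.** If every time is cut at a common horizon h, the group coefficient is a difference in restricted mean time to h, and its value depends on h. For illustration, assume a constant hazard λ, so that the restricted mean is (1 − exp(−λh))/λ. The two Control figures do not fit one constant hazard (50% at 12 months implies 35% at 18), so both calibrations are shown.

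- λ = −ln(0.40)/18 = 0.0509 for Control, 0.0407 for Intervention. h = 18: 12.76 − 11.79 = 0.97 months. h = 12: 9.49 − 8.98 = 0.51 months.
- λ = ln 2/12 = 0.0578 for Control, 0.0462 for Intervention. h = 18: 12.22 − 11.19 = 1.03 months. h = 12: 9.21 − 8.66 = 0.56 months.

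The hazard ratio is 0.8 throughout, but the linear coefficient roughly halves if follow-up ends at 12 months instead of 18. The 12-month horizon is only an example, since the SAP gives no date for the interim analysis. If only leavers were analysed, simulation under the first calibration gives a difference of about 0.27 months. The sentence in section 9.1 does not choose between these quantities.

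**Step 3: secondary outcomes set against the stated model.**

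- Yes/no: satisfied, feels valued, likely to stay; having been approached also reads as yes/no. At a fitted probability p the residual can only be 1 − p or −p, so it cannot be normal. Its variance p(1 − p) changes with p, so ordinary standard errors are not justified in general.
- Nominal: reasons for leaving. Linear regression does not apply.
- Continuous or nearly so: THRIVE scores on 0–100 and change in wage. Linear regression is reasonable here.

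**The case against.** Much can be said for the plan.

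- **The main result is safe.** The arms are compared by Cox regression, and the adjusted Cox model already carries most candidate determinants (age, tenure, self-efficacy, factory location, residence, family status, skill grade, attendance). For retention, the linear analysis is supplementary. This stands and limits the point.
- **A restricted-mean reading is available.** Section 4.6.1 takes employment status from the company database from entry to closure, section 4.8 says the sample cannot suffer attrition, section 4.10.2 has weekly assessment over 18 months, and section 8.3 expects minimal loss. If all goes to plan, linear regression of time cut at 18 months estimates a legitimate quantity. This stands in large part. But the SAP states no such estimand or horizon, sections 4.5 and 4.11 allow early termination, and section 8.1 counts withdrawals. How likely these are is not given.
- **A linear model for a yes/no outcome estimates a risk difference.** It is usable with robust standard errors. The SAP does not specify them, and its normality checks still do not apply.
- **The sentence may be loose drafting for regression in general.** Possibly, but section 2 commits the report to follow the plan, and a literal reader would fit the wrong model.

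A reader might infer more than the documents support. One might call the linear coefficient biased toward zero by comparing it with a difference in mean total job duration. The SAP never names that quantity as a target, and it would need extrapolation beyond 18 months, so the gap would be between two estimands and would not measure bias. Nor does the size of a failed Shapiro-Wilk test measure harm: with 1,260 workers, inference on linear coefficients does not hinge on normal residuals.

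**Conclusion.** The point holds as a mismatch between a stated model and stated outcomes, outside the primary comparison. On the SAP's own assumptions about 44% of the retention times would be censored, and the linear determinants models have no stated horizon, estimand or rule for censoring if the trial stops early or workers withdraw. At least three secondary outcomes are yes/no, with no binary-outcome model named, no robust errors specified and normality checks that cannot apply.

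The 44% rests on 40% Control retention at 18 months and a proportional hazard ratio of 0.8. The horizon illustration also assumes a constant hazard. It would go too far to conclude that the treatment effect on retention is wrongly analysed, or that linear and Cox results must disagree: under the design assumptions both favour Intervention. Linear regression remains suitable for the continuous secondary outcomes. This should be corrected, but it does not threaten the primary hazard ratio.

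**What to change.** Replace the general sentence in section 9.1 with a model for each type of outcome:

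- **Determinants of retention:** Cox regression, so that censoring is handled and the group effect is on the same scale as the primary result.
- **Yes/no secondary outcomes:** logistic or modified Poisson regression, or a risk-difference model with robust standard errors. Name one in advance.
- **Continuous outcomes,** such as the THRIVE 0–100 scores and wage change: keep linear regression.
- **Normality checks:** restrict them to these continuous outcomes.

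If a result in months of employment is wanted as well, state it as a restricted mean at a named horizon, with a method that allows for censoring.

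The cost is a wording change. No extra data or participants are needed, and the models are standard in the named software, Stata 18.
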